During the third week of the evaluation period, subjects will attempt to abstain from smoking for a five day period and will be seen daily to determine smoking status. These visits will occur on five consecutive days with the visits in most instances occurring Monday through Friday. Subjects will be told to smoke normally until the evening prior to the first of the abstinence assessment days and then to attempt to not smoke at all during the subsequent five days. At each visit, smoking status will be evaluated by measuring exhaled carbon monoxide (CO) concentrations with a value of < 5 ppm confirming abstinence. Each visit during this week will be scheduled in the afternoon in order to assess mid-day CO rather than CO after just waking up. Subject will stop taking medication after they complete their five consecutive days of study visits.

The same procedures will then be repeated except that subjects will receive the alternate treatment. Since continued participation in the study will require subjects to resume smoking, subjects will be told that it is not necessary for them to resume smoking if they wish to remain abstinent; however they would not be able to continue participation in the study if this were the case. At the conclusion of the study, subjects will be given information about resources in the community that could assist them with the smoking cessation attempt. They will additionally be called by telephone approximately 1 week after completing the study in order to ensure that there are no adverse events and to ascertain if they have attempted to quit smoking. Those that have not made a cessation attempt will be encouraged to do so and will again be provided with information regarding community resources to assist them.

Subjects will therefore be seen at a screening visit and at 9 visits per study period for a total of 19 visits.

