e) Outcome Measures: The primary outcome measure is the number of days of confirmed abstinence during the third week of each assessment period (out of a maximum of 5 days). A secondary outcome is the percentage of subjects who are abstinent at all five cessation visits.

Additionally at each visit, subjects will complete the Minnesota Nicotine Withdrawal Scale (MNWS), the Subjective State Scale (SSS) and the Questionnaire of Smoking Urges (QSU-Brief). Subjects will also be asked to report any adverse events they have experienced. The Minnesota Nicotine Withdrawal Scale, is a widely used scale to assess nicotine withdrawal symptoms.¹⁵ The positive affect and distress subscales of the SSS, have been found to be reliable at assessing these mood symptoms (alphas are 0.85 and 0.82, respectively).¹⁶ The Brief version of the Questionnaire of Smoking Urges (QSU-Brief) is a commonly used scale to assess nicotine craving with a score for each of two factors (i.e. intention and desire to smoke,

anticipation of relief from negative affect) calculated in order to examine several aspects of the urge to smoke.¹⁷

5 Potential Risks of Study Participation and Protection Against Risk

a. Risks to subjects: Levomilnacipran is generally well tolerated with the most common side effects reported being nausea / vomiting, constipation, excessive sweating, increased heart rate, urinary hesitation, palpitations and erectile dysfunction. Although occurring rarely other side effects including but not limited to mania, rash and allergic reaction, mydriasis, increases in blood pressure and abnormal bleeding have been occasionally reported. There is the possibility that when discontinuing levomilnacipran, subjects may experience a withdrawal syndrome that includes symptoms of dizziness, nausea and paresthesias. Questionnaires will be used to assess a variety of measures to ensure eligibility for the study and to measure outcomes of interest such as cigarette craving and withdrawal symptoms. Some of these questionnaires may ask questions that subjects would consider personal.

As with any medication, there is a risk that unanticipated side effects may occur.

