a.4) Data analysis: A paired t-test will be used to test treatment effect based on days of abstinence per quit assessment week (range 0-5, not necessarily consecutive) between levomilnacipran and placebo. Additional separate analyses for menthol and non-menthol cigarette smokers will be conducted. A two-sample t-test will be used to compare the difference in days of abstinence per quit assessment week for menthol cigarette smokers compared to non-menthol cigarette smokers.

Repeated measures Analysis of Variance (ANOVA) will be used for days of abstinence per quit assessment week, assuming mixed effects three-factor ANOVA model (“Order of phases” with two levels, “Treatment” with two levels, “Menthol cigarettes smoker” with two levels, subject effects are random); then use contrasts to compare treatment with placebo for all participants and for menthol cigarette smokers and non-menthol cigarette smokers separately. This approach allows us to investigate primary and secondary aims simultaneously, therefore, to potentially achieve higher statistical power. The use of paired t-tests, on the other hand, provides a proper tool for sample size determination as seen in the following section.

Generalized estimating equation (GEE) model will be used to analyze the longitudinal data, with the number of subjects able to maintain continuous abstinence on all 5 days throughout the quit week as the secondary outcome. Treatment effect (levomilnacipran vs. placebo) and cigarette type effect (menthol vs. non-menthol) will be estimated.

Secondary variables such as scores on the MNWS, SSS and QSU-Brief will be summarized by the mean, standard deviation, median and range. The change in these measures occurring between baseline (i.e. the first week of treatment) and the last day of the third week will be compared between drug and placebo. Similar two-factor ANOVAs will be used to analyze each of the calculated differences as the primary endpoint. Additionally, frequency of subject reported adverse events will be compared between treatments via the use of paired t-tests.

a.5) Power Consideration: The adequacy of planned sample sizes are assessed using two-sided paired t-test. We tested the “minimum detectable difference”, expressed as the number of standard deviations (i.e. “effect size”) for several sample sizes where the two-sided paired t-test is pre-set at a 5% significance level and 80% power. The variability is based on estimates found

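### Withdrawal, mood and craving scales are compared between treatments on the last quit day only, and that contrast cannot be read as withdrawal relief because it includes the drug's effect on abstinence

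*Combined protocol and SAP*

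**What the plan says.** Section 4 e) sets the collection schedule: "Additionally at each visit, subjects will complete the Minnesota Nicotine Withdrawal Scale (MNWS), the Subjective State Scale (SSS"), and QSU-Brief alongside them. Section 4 c.2) describes the quit week: "subjects will attempt to abstain from smoking for a five day period and will be seen daily to determine smoking status". On the timing it adds "These visits will occur on five consecutive days", with exhaled CO measured at each visit.

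Section 6 a.4) gives the scales two uses. First, the scores "will be summarized by the mean, standard deviation, median and range"; it does not say which days this covers. Second, the change "between baseline (i.e. the first week of treatment") "and the last day of the third week will be compared between drug and placebo", using two-factor ANOVAs whose factors are not named. Nothing in a.4 restricts, stratifies or adjusts this comparison by smoking status on the last day. The GEE model in the same section concerns continuous abstinence, not the scales.

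**The concern.** The scales are meant to show how subjects feel when they try not to smoke. Section 4 a) itself treats withdrawal symptoms as something abstinence induces, and section 6 a.3) hypothesises that the drug increases abstinent days. If both are true, the drug changes who is abstinent on the last day as well as how abstinent subjects feel. For withdrawal, these two effects push the mean score in opposite directions.

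Last-day scores will come from both smokers and abstainers. Abstinent days need not be consecutive (6 a.4), and the attendance bonus does not depend on quitting (section 4, payment), so subjects who smoke are expected to keep attending.

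The specific aim in section 2 is framed as a question of mechanism, and these are the only planned measures of withdrawal, mood and craving. A null or adverse last-day difference could be misread as evidence that the drug does not ease withdrawal. The plan also relies on a single day when five are available.

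**Working it through.** **1. The plan's own figure.** The power section (6 a.5) gives one detectable effect, 0.57 SD, for abstinent days. It gives none for the scales. A two-sided paired t-test at 5% and 80% power (noncentral t) gives 0.572 SD at n = 26 and 0.396 SD at n = 52. The 0.57 is thus reproduced, as the figure for one cigarette-type group. Nothing below depends on it.

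**2. Scores available and used.** Section 4 c.2) gives 2 baseline, 2 titration and 5 quit-week visits per period: 2 + 2 + 5 = 9, which matches "Subjects will therefore be seen at a screening visit and at 9 visits per study period". Of the 5 quit-week scores per period, the treatment comparison uses 1 and leaves 4.

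**3. Precision from using all five.** Assume equal variance s², one baseline score, and the same correlation ρ between any two scores.
- Last-day change: s²(1 + 1 − 2ρ) = 2s²(1 − ρ).
- Five-day-mean change: s²[(1 + 4ρ)/5 + 1 − 2ρ] = 6s²(1 − ρ)/5.
- Ratio: (6/5)/2 = 0.60 at any ρ. The detectable difference is multiplied by √0.60 = 0.77.

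The equal-correlation assumption matters. If quit-week scores correlate ρw with each other and ρb with baseline, the ratio is [1 + (1 + 4ρw)/5 − 2ρb]/(2 − 2ρb). With assumed ρw = 0.8 and ρb = 0.5 this is (1 + 0.84 − 1)/1 = 0.84. There is a gain in both cases, but 0.60 is not guaranteed.

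**4. What the last-day contrast measures.** Let abstinent subjects score W above those smoking, let the drug cut that excess by a fraction k, and let pD and pP be the proportions abstinent on the last day on drug and placebo. The mean drug-minus-placebo difference is

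W[pD(1 − k) − pP],

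so the drug looks worse whenever k < 1 − pP/pD. W, k, pP and pD are all assumptions; the documents give none of them.

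| pP | pD | Break-even k | k = 0 | k = 25% | k = 50% |
|---|---|---|---|---|---|
| 20% | 40% | 50% | +0.20W | +0.10W | 0 |
| 30% | 60% | 50% | +0.30W | +0.15W | 0 |
| 30% | 50% | 40% | +0.20W | +0.075W | −0.05W |
| 30% | 40% | 25% | +0.10W | 0 | −0.10W |
| 30% | 35% | 14% | +0.05W | −0.04W | −0.125W |

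**5. How often this would reach significance.** A simulation used 4,000 runs, 52 completers, W of about 1 SD, a paired t-test on last-day scores, and abstinence drawn independently of the underlying score. About 2.5% of runs would show significant worsening by chance.
- 20% v 40%, k = 0: significant apparent worsening in 23% of runs.
- 20% v 40%, k = 25%: 9%.
- 20% v 40%, k = 50%: mean difference about 0, and worsening at about the chance rate.
- 30% v 60%, k = 25%: 16%, falling to 7% if W is halved.
- 30% v 35%, k = 25%: mean difference −0.04 SD, the correct direction.

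**6. Does averaging remove this?** No. For a five-day mean the same expression applies, with pD and pP replaced by their averages over the five days. Averaging changes precision, not what is being estimated.

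**The case against.** The strongest reply is that the planned contrast is not biased. Treatment order is randomised and all subjects are compared, so it estimates the total effect of the drug on last-day scores. Abstinence is a mediator of that effect, not a confounder. This stands: the fault lies in leaving the interpretation unstated, not in the test.

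A reader might infer that an effective drug will appear to worsen withdrawal. The documents do not support that. They give no score gap and no last-day abstinence rates, and the table shows that the direction depends on both and on the amount of relief. Reversal is possible, not established. Nor does one direction hold for all three scales: SSS has a positive-affect subscale that would be expected to run the other way, and craving may be high in subjects who lapse.

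A reader might also infer that the other four days' scores are discarded. The descriptive summary is not limited to one day, so they are unused only in the treatment comparison.

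Adjusting for smoking status has its own weakness. It conditions on something that happens after randomisation, and subjects who stay abstinent on placebo may be those with mild withdrawal. Nor is the week-2 visit wholly free of the problem: subjects are told to smoke normally, but a drug may still reduce smoking, and that visit does not measure the response to quitting.

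Finally, this is a pilot, the scales carry no hypothesis in 6 a.3), and section 4 a) says that tests of withdrawal blunting predict efficacy poorly. That limits the severity, but does not justify leaving the scores out of the comparison.

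**Conclusion.** The point holds as one of efficiency and interpretation. The text is clear that the only treatment comparison of the scales is the change to the last quit day, over all subjects, with no reference to smoking status. Using all five scores reduces the variance of the change to 0.60 under equal correlations and one baseline score, and by less if quit-week scores correlate more strongly with each other than with baseline.

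As it stands, the contrast cannot be read as withdrawal relief. Relief can be masked, or reversed when the drug's proportional cut in withdrawal is smaller than 1 − pP/pD. The size cannot be derived from the documents, and the argument is firmest for MNWS. The abstinence outcomes are untouched, so this is a low-severity improvement to the secondary scale outcomes.

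**What to change.** In section 6 a.4):

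- Replace the last-day score with all five quit-week scores in the all-subject contrast, either as the five-day mean or as daily scores in the repeated-measures model.
- State that this contrast is a total effect and includes whatever the drug does through abstinence.
- Add, labelled supportive, the same contrast with same-day CO-verified smoking status as a time-varying factor. Note that it conditions on a post-randomisation variable and is open to selection.
- Add, also as supportive, the change to the last week-2 visit, when subjects are on treatment and instructed to smoke normally in both periods.
- Name the baseline visit or visits. The wording in a.4 ties baseline to treatment, whereas sections 4 b) and c.2) place baseline in week 1, before medication starts. The week-2 contrast needs this reconciled.

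The cost is a few sentences in the analysis plan and modest analysis work. No new data or visits are needed.

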In a series of three papers, this method was used to test four medications. Three of the medications tested are known to increase smoking cessation rates (i.e. nicotine patch, bupropion, varenicline) and one medication tested is known to not increase smoking cessation rates (i.e. modafanil). Number of days abstinent (the primary outcome) was significantly higher during use of all three effective medications relative to placebo thereby demonstrating this method's sensitivity.⁴⁻⁶ The number of days abstinent was not different between modafanil and placebo thereby demonstrating this method's specificity.⁵ By examining motivation to quit on outcomes, the developers of this method found that the best results were obtained when those interested in cessation were recruited for studies using these methods.

In order to determine if levomilnacipran is potentially effective at increasing smoking cessation rates, we will use the medication testing methods described and validated by Perkins et al.³

b) Study Design Overview: We will utilize a cross-over, double-blind study design. Three weeks of the study will be to evaluate levomilnacipran and three weeks will be to evaluate placebo with the two evaluation periods occurring in random order (i.e. one-half of the subjects will receive levomilnacipran followed by placebo, whereas the other half will first receive placebo followed by levomilnacipran). The first week of each three week evaluation period will be to obtain baseline values, the second week to titrate medication and the third week to evaluate efficacy. In order to determine if effects of levomilnacipran depend on the type of cigarettes smoked (i.e. menthol vs. non-menthol), we will enroll an equal number of those smoking each type of cigarette.

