To ensure confidentiality, all subjects enrolled in the study will be assigned a study identification code. These codes will be used on all study related data collection forms except for those on which the use of personal identifiers is mandatory (e.g. informed consent form). Forms that link the name of the participant and the subject identification code will be kept in a locked cabinet or office or in an electronic file stored on password protected computer servers meeting University guidelines. Access to subject identifiable information will be limited to those that require this information such as study investigators or others who have direct contact with study subjects (e.g. study coordinator).

6 Statistical Analysis

a. Statistical Methods of Data Analysis

a.1) Statistical Design: A within-subject cross-over design will be used for the study in which smokers will receive levomilnacipran and placebo (double-blind) with the order of treatment being randomly assigned. The primary aim is to compare the number of abstinent days between levomilnacipran and placebo by type of cigarette smoked (menthol cigarette and non-menthol cigarette). A secondary aim is to compare levomilnacipran responses between menthol cigarette smokers and non-menthol cigarette smokers.

a.2) Outcome Variables and Measurements: The primary outcome is the number of days abstinent during the third week of each assessment period as assessed by self-report of no smoking that day and verified by an exhaled carbon monoxide (CO) concentration of <5 parts per million. A secondary outcome is the percentage of subjects who are abstinent at all five cessation visits. The other outcomes include ratings on the Minnesota Nicotine Withdrawal Scale (MNWS), the Subjective State Scale (SSS), the Questionnaire of Smoking Urges (QSU-Brief) and frequency of reported adverse events.

a.3) Hypotheses: The following hypothesis will be tested: 1) Levomilnacipran increases the number of abstinent days vs. placebo. This hypothesis will then be tested separately for smokers of menthol cigarettes and for smokers of non-menthol cigarettes. 2) A secondary hypothesis is that the increase in number of abstinent days will be lower in smokers of menthol cigarettes than in smokers of non-menthol cigarettes (i.e. levomilnacipran will be less effective in smokers of menthol vs. non-menthol cigarettes).

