in the literature by others using these methods.⁵ With a total of 52 subjects completing the study (26 menthol smokers and 26 non-menthol smokers), we are able to detect an effect size of 0.57 standard deviations for the comparisons between levomilnacipran and placebo which is considerably smaller than the effect size of approximately 1.65 reported by Perkins et al for bupropion.⁵ Since we anticipate a 20% attrition rate, we are planning on enrolling 64 smokers in total (32 smokers of menthol cigarettes and 32 smokers of non-menthol cigarettes).

7 Data and Safety Monitoring Plan (DSMP)

The principal investigator in conjunction with the study physician will be responsible for monitoring adverse effects. At the conclusion of each visit subjects will be asked whether they have had any side effects. Any positive response will be followed up with questions regarding details of what the adverse effect was and the severity. To the extent possible, each adverse event will be evaluated to determine 1) its severity (mild, moderate, severe), 2) its relationship to the study medication; 3) its duration and 4) whether it constitutes a serious adverse event.

The participation of any subject will be discontinues if they develop a side effects of greater than moderate severity (as determined by the investigators) or develops any symptoms that in the opinion of the investigators would warrant discontinuation from the study. Participation in the study would also be discontinued if during the course of the study the subject develops a significant medical condition (regardless of whether it can be attributed to the study drug) or is initiated on medication that can be expected to interact with the measures being assessed or increase the risk of being on the study medication. The subject has the option of discontinuing their participation at any time for any reason. Adverse events will be reported to the IRB as required per IRB guidelines.

8 References

1. Fiore MC, et al. *Treating tobacco use and dependence: 2008 Update. Clinical Practice Guidelines. U.S. Department of Health and Human Services. Public Health Service*. Rockville, MD2008.
2. Hughes JR, et al. Antidepressants for smoking cessation. *Cochrane Database Syst Rev*. 2014;1:CD000031.
3. Perkins KA, et al. An efficient early phase 2 procedure to screen medications for efficacy in smoking cessation. *Psychopharmacology (Berl)*. 2014;231:1.

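### The planned paired t-test for adverse events leaves out subjects stopped in their first period for a more-than-moderate side effect, about half of such events

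*Combined protocol and SAP*

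**What the plan says.** Section 6 a.2 lists "frequency of reported adverse events" among the other outcomes. Section 6 a.4 gives the method: "frequency of subject reported adverse events will be compared between treatments via the use of paired t-tests". No safety analysis set is named, and nothing says how a subject with only one treated period enters this comparison. No unpaired or severity-specific summary is planned.

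Section 7 governs collection and stopping. On collection: "At the conclusion of each visit subjects will be asked whether they have had any side effects". As far as possible each event is then assessed for "1) its severity (mild, moderate, severe), 2) its relationship to the study medication", and also for duration and seriousness. On stopping: "The participation of any subject will be discontinues if they develop a side effects of greater than moderate severity". Participation also ends if "the subject develops a significant medical condition (regardless of whether it can be attributed to the study drug").

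Section 4 b sets the order of treatments: "one-half of the subjects will receive levomilnacipran followed by placebo", and the other half the reverse. Section 6 a.5 plans 64 enrolled and 52 completing.

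**The concern.** A paired t-test works on within-subject differences, so a subject without a second period has no difference to contribute. Most reasons for leaving early have no direct link to the safety outcome. This one does: the subject leaves because of the quantity being compared. The milder events that the same subject reported before stopping leave the test as well.

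Tolerability is part of the case for this drug. Section 1 says that nortriptyline is held back by its adverse effects and looks for better-tolerated agents of the same class. Section 3 presents levomilnacipran as lacking many of nortriptyline's side effects. A comparison depleted of first-period severe events is a weak basis for any statement on that point.

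**Working it through.** **The plan's own figures.** None is given for adverse events. The "two-sided paired t-test is pre-set at a 5% significance level and 80% power" belongs to days of abstinence. Its detectable effect of 0.57 SD reproduces as 0.572 with n = 26, one cigarette-type group. Enrolment is 52 / 0.80 = 65, against 64 stated, which is close enough. I use 64 as the input here.

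**Inputs from the documents.** 64 enrolled, split equally between the two orders: 32 drug-first and 32 placebo-first.

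**Assumed inputs.** Let d and p be the probabilities of a more-than-moderate event in a drug period and in a placebo period. Let o be first-period dropout for other reasons, 0% or 10%. Events in the two periods are taken as independent. A subject stopped in the second period is taken to keep the shortened second-period value and so to form a pair.

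**Formulas.**
- Drug events lost (drug-first subjects, first period): 32 × d
- Drug events kept (placebo-first subjects, second period): 32 × (1 − p) × (1 − o) × d
- Share of drug events lost: 1 / [1 + (1 − p)(1 − o)]
- For placebo, exchange d and p.

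**Results with o = 0.**

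| d / p | Drug lost | Drug kept | Placebo lost | Placebo kept | Excess on drug, all periods | Excess on drug, pairs only |
|---|---|---|---|---|---|---|
| 2% / 1% | 0.64 | 0.63 | 0.32 | 0.31 | 0.64 | 0.32 |
| 10% / 2% | 3.20 | 3.14 | 0.64 | 0.58 | 5.12 | 2.56 |
| 15% / 3% | 4.80 | 4.66 | 0.96 | 0.82 | 7.68 | 3.84 |

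The share lost at 10% / 2% is 1 / 1.98 = 51% on drug and 1 / 1.90 = 53% on placebo. Across the three rows, with o at 0% or 10%, it runs from 50% to 53% on drug and from 51% to 57% on placebo.

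**As a rate, at 10% / 2%.** The number of pairs is 32 × 0.90 + 32 × 0.98 = 60.16. The paired difference in more-than-moderate events is 2.56 / 60.16 = 4.3 percentage points. The assumed true difference is 8.

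**Effect on the planned outcome, which counts events of every grade.** A simulation of 5,000 trials at 10% / 2%, with non-severe means also assumed (1.0 events per drug period, 0.6 per placebo period), gives a mean difference of 0.49 events using all treated periods and 0.43 using pairs.

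**The case against.** The strongest reply is that little is at stake. This is a pilot of an approved drug, dosed for 12 days at what Section 5 b calls the lowest recommended dose for depression. Adverse events carry no hypothesis in Section 6 a.3, and no efficacy conclusion depends on this test. If only 1% of subjects had a more-than-moderate event on drug, the expected loss would be 32 × 0.01 = 0.3 subjects. Total event frequency moves much less than severe events do: 0.49 to 0.43 in the simulation. All of this stands and limits the weight of the point. It does not supply a rule for single-period subjects.

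Four stronger readings are tempting, and the documents do not support them.

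- *All severe events drop out.* A subject stopped in the second period already has first-period data and a shortened second-period value, so a pair can be formed. Total loss would need an analysis restricted to completers. The 52 completers belong to the power calculation, and a.4 does not restrict the adverse-event comparison to them.
- *No one who completes can have had such an event.* One may be first reported at the last abstinence visit, or in the telephone call about a week after completion (Section 4 c.2).
- *The data are discarded.* Section 7 ends participation, not the record. Events are assessed and go to the IRB as its guidelines require. What is lost is a place in the comparison.
- *The t-test is unsuitable for such data.* On yes/no events in 52 pairs its exact error rate is 1.5% to 5.3% when 4% to 40% of pairs are discordant. It becomes conservative for rare events (0.2% at 2% discordance) but is not materially inflated. The missing pairs are the problem, not the distribution.

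**Conclusion.** The point holds for subjects stopped in the first period. The only planned adverse-event comparison excludes them because of the outcome it compares, and nothing else in the plan makes up for this. The loss is about half of the more-than-moderate events on each treatment. That fraction follows mainly from the 1:1 order and depends little on the rates. The absolute number does depend on them: about 0.6 to 4.8 drug-first subjects at assumed rates of 2% to 15%.

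The direction is conditional. With equal rates on both treatments, the two sides lose alike and the expected difference is not shifted. If levomilnacipran has the higher rate, the excess of severe events is roughly halved and the comparison flatters the drug. The documents give no rates, so this is plausible, not shown. The point concerns a safety summary and leaves the abstinence analysis untouched. It should still be corrected before analysis, because the remedy is cheap.

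**What to change.** Replace the paired t-test sentence in Section 6 a.4 with a plan along these lines:

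- **Analysis set:** everyone who took at least one dose in a period, using every treated period. Each event is assigned to the treatment being taken when it arose.
- **Overall frequency:** a GEE or mixed model with treatment and period terms that keeps single-period subjects. Name one outcome in advance: any event (logistic), or number of events (Poisson, with an offset for days on treatment, so that periods cut short are handled).
- **Severe events:** tabulate more-than-moderate events and side-effect discontinuations by treatment, descriptively, because they will be too few to model.
- **Supportive:** a paired analysis may be kept, labelled as restricted to subjects with both periods.

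The discontinuation rule stays as it is. The cost is a change of SAP wording and slightly more analysis work. Event details are already collected under Section 7, and a.4 already uses GEE for continuous abstinence.
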